### Per Protocol Analysis

As a secondary analysis, the primary outcome of clinical malaria will also be analysed per protocol (PP). The PP population will be defined separately for each year of the study. Children who were vaccinated at all scheduled vaccination contacts in a particular year (3 in 2017, 1 in each subsequent year) and who, in the same year, were also seen at the first SMC/SMC placebo contact each month (4 per year) will be considered as 'per protocol' for that year.

Children who attended for SMC administration but who did not receive SMC because they had malaria and were referred for treatment will be included in the per protocol analysis.

'Per protocol' is defined differently for the two interventions (vaccination and SMC). For vaccination, a child must have *received* all vaccination doses that year; for SMC a child must only have *attended* all SMC contacts that year. This difference is necessary because the primary outcome of the trial (clinical malaria) can result in a specific SMC dose being missed permanently, whereas if a child had malaria at the time of vaccination, catch-up was attempted later in the season. The per protocol conditions will be applied equally to all three groups, i.e. to be considered as per protocol, a child must have received all doses of vaccine AND attended all SMC contacts, irrespective of which of these were active and placebo.

All secondary outcomes will be analysed by modified intention to treat, as described above.

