### **2.3.2 Progress with the trial**

In Burkina Faso, 92% of enrolled children received all three priming doses of RTS,S/AS01E or control (rabies) vaccine in 2017, 90% received their first booster dose in June 2018 and 90% received their second booster dose in June 2019. In Mali, 93% of children received all three priming doses of RTS,S/AS01E or comparator vaccine in 2017, 88% received their first booster dose of vaccine in June 2018 and 85% their second booster dose of vaccine in June 2019. Coverage with SMC or placebo has been high throughout the trial with nearly 90% of children receiving all four monthly SMC courses during the first and second years of the study. Retention of children in the trial has also been high. At a census undertaken early in 2019, 2547 (92%) of the 2777 children enrolled in Burkina Faso and 2816 (90%) of the 3143 children initially enrolled in Mali were still contributing to the study.

The investigators remain blind to the randomisation code. However, in March 2019 members of the trial's Data and Safety Monitoring Board (DSMB) met to review safety outcomes during the first two years of the trial. They reviewed data on deaths, deaths attributed to malaria, hospital admissions and hospital admissions attributed to malaria broken down by study group. The board concluded that it was safe for the trial to continue for a third year retaining the three initial study groups. This recommendation implies that during 2018 a single booster dose of RTS,S/AS01E was not markedly inferior to SMC in protecting against the outcomes considered by the board and provided encouragement for continuation of the trial into a third year and, potentially, for longer.

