### **7.5 Seasonal Malaria Chemoprevention (SMC)**

Four or five courses of SMC with SP+AQ will be given at monthly intervals during the malaria transmission season to children in the SMC alone and SMC +RTS,S/AS01E groups. A course of SMC for children aged over the age of one year comprises a single treatment of SP (500mg/25 mg) and AQ 150mg on day 1 and AQ 150mg on days 2 and 3. SP and AQ and matching placebo will be obtained from Guilin Pharamceuticals, Shanghai, Co, a GMP-certified supplier. All treatments will be given under observation. SP can cause Stevens-Johnson syndrome, but this side effect has been seen very rarely when SP has been used for either intermittent preventive treatment of malaria in pregnancy or SMC. Amodiaquine is bitter and may cause vomiting but serious side effects, which include liver damage and neurological side effects, are very rare. SMC with SP+AQ has proved to be very safe. A study conducted in Senegal in which the consequence of administration of 800,000 doses of SMC with SP+AQ were followed carefully identified only three serious potentially drug related adverse effects (two cases of hepatic damage and one extra-pyramidal syndrome) [11]. Enhanced pharmaco- vigilance in 7 countries participating in the ACCESS-SMC project funded by UNITAID, through which approximately 15 and 30

million treatment courses were administered in 2015 and 2016, respectively, has confirmed that SMC with SP+AQ is very safe.

SMC drugs will pre-packed by a pharmacist, who takes no further part in the trial, in re-sealable envelopes bearing the child's unique number and containing tablets for the four cycles of treatment required for one malaria transmission season. Treatment with each dose of SMC is given by trained, paid volunteers at a central point in each study community under observation. Study children will be given an updated identity card containing their photo, study identity number and date of birth. At the time of vaccination and/or SMC administration, a child's photo ID card is scanned to ensure that the child is given the allocated intervention. Home visits are made to children who miss treatment on the designated day and their parents/guardians are asked if they would still like their child to receive SMC. If they agree, treatment is given at home.

The interventions that children in each study group will receive during the extension period are summarised in Table 1.

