| June 2020                       | Tetanus (BF) or
Tetanus/Diphtheria
toxoids (Mali) x 1 # | RTS,S/AS01 E x 1                        | RTS,S/AS01 E x 1                                |
| July-Oct 2020                   | SMC x 4  | SMC placebo x 4                                    | SMC x 4  |
| June 2021*                      | Tetanus toxoid x 1 #  | RTS,S/AS01 E x 1                        | RTS,S/AS01 E x 1                                |
| July-Nov 2021* \$    | SMC x 4
(Mali)  | SMC placebo x 4
(Mali)                          | SMC x 4
(Mali)  |
|                                 | SMC x 5
(Burkina Faso)  | SMC placebo x 5
(Burkina Faso)                  | SMC x 5
(Burkina Faso)                                  |

\* Only children aged 5 years or below on June 1st 2021 were eligible to receive study intervention in 2021.

# In 2020, due to difficulties shipping tetanus toxoid vaccine from India as a result of the COVID-19 outbreak, children in group 1 in Burkina Faso received tetanus toxoid vaccine from stocks held by Burkina Faso's national infant immunization programme. Children in group 1 in Mali received tetanus/diphtheria toxoids vaccine from stock held by Mali's national infant immunization programme. In 2021, children in both countries received tetanus toxoid vaccine supplied by the Serum Institute of India.

\$ In Burkina Faso, in 2021, the National Malaria Control Programme began to deliver 5 monthly courses of SMC in the study area. To ensure that our intervention reflected the current standard of care, the study team also administered 5 SMC courses in 2021.

**Figure 1.** Schematic of Key Study Activities in the Initial Trial Period, and in the Two-Year Extension

Only children aged below 5 years on June 1st 2021 were eligible to receive study intervention in 2021.

**Precise timing of interventions during the original trial, and the extension study***Administration of RTS,S/AS01E or control vaccine:*

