## Extension study:

In 2020, SMC was administered to all children, as four monthly courses, starting in July. In 2021, all children exactly five years of age, or below, on 1st June 2021 received SMC, starting in July 2021. In Mali, children received four courses of SMC in 2021. In Burkina Faso, children received 5 cycles in 2021, because the national programme decided to deliver five cycles of SMC in Houndé district.

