### **Trial Profile - Extension Study**

The number of individuals eligible to join the two-year extension study, and the number who gave consent to participate will be shown.

The number of children who exited the study population by the end of the fourth (2020 intervention year) will be tabulated with reasons (where known) indicated.

Children who reached the age of 5 years prior to the 2021 intervention year will be shown as a separate category (this does not count as 'loss to follow-up' as these children were excluded from further intervention by design, and continued to be monitored for longer-term for morbidity post-intervention).

Among children who remained below the age of five years in June 2021, the number of children who exited the study population by the end of the fifth (2021 intervention year) will be tabulated, with reasons (where known) indicated.

Uptake of the study interventions during the intervention period will be summarised, including:

- the number that received different combinations of vaccine doses;
- the distribution of the interval between doses;
- the number that received 0,1,2,3,4 (and 5 in Burkina Faso, in 2021) SMC treatments each year;
- the actual timing of SMC cycle 1 in relation to the malaria transmission season;
- the mean and range of the intervals between the monthly SMC courses;
- the adherence to daily doses of SMC each month

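### The SAP per-protocol rule counts four SMC contacts a year, but five were scheduled and given in Burkina Faso in 2021

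*Combined protocol and SAP*

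**What the plan says.** The SAP section Per Protocol Analysis defines per-protocol status separately for each study year. A child must have been vaccinated at every scheduled vaccination contact that year, with the number spelled out by year (three in 2017, one in each later year). The child must also be among those who "were also seen at the first SMC/SMC placebo contact each month (4 per year"). The SMC count carries no exception. Later in the section the condition is restated in words: "a child must have received all doses of vaccine AND attended all SMC contacts".

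The rest of the SAP gives a different number for one country and year. The footnote to Table 1 (Study Interventions) says of Burkina Faso that "the study team also administered 5 SMC courses in 2021". The section on timing of administration says "In Burkina Faso, children received 5 cycles in 2021". The uptake summary in Trial Profile - Extension Study was written to allow for this: "the number that received 0,1,2,3,4 (and 5 in Burkina Faso, in 2021) SMC treatments each year". The protocol tables in the Protocol Summary and section 7.5 schedule the same five courses.

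Protocol section 10.2 defines the per-protocol set by receipt of all scheduled SMC doses and fixes no number.

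**The concern.** An analysis population should be reproducible from its definition. For Burkina Faso in 2021, the section contains two instructions that classify the same child differently. A younger child who attended contacts one to four and missed the fifth satisfies the bracketed count but fails the requirement to attend every contact. A programmer may well code the explicit number, because it is the easier of the two to implement.

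The reference to each month does not settle the matter. The SAP descriptions of the three groups place the five Burkina Faso rounds between July and October 2021, which is four calendar months, while the tables say July to November.

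Study Year 5 is analysis period C, one of the three periods for which the SAP plans hypothesis tests. The per-protocol analysis that supports it should rest on a set that two analysts would derive identically.

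A related clerical slip concerns the same fifth course. In the protocol's Schematic of Study Design, Table 1 gives the combined group in Burkina Faso in 2021 five courses of SMC placebo. The Protocol Summary, section 7.5 Table 1 and the SAP all give that group five courses of active SMC.

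**Working it through.** **1. Count of scheduled contacts.** The plan's own figure is four per year. Setting it against the schedules:

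| Country and years | Scheduled SMC/placebo contacts | Agrees with the rule's count |
|---|---|---|
| Both countries, 2017 to 2020 | 4 per year | yes |
| Mali, 2021 | 4 | yes |
| Burkina Faso, 2021 | 5 | no |

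The figure is right everywhere except Burkina Faso in 2021.

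**2. Slip or choice?** Nothing in the documents says the fifth contact was meant to be left out. The vaccination bracket in the same sentence varies by year, so the brackets are meant as exact yearly counts. The uptake list for the original study stops at four treatments; its extension counterpart adds the fifth for Burkina Faso. The per-protocol bracket did not receive the same update.

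**3. Illustrative size.** The documents give no attendance data for Burkina Faso in 2021, so these inputs are assumptions:

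- Attendance at the first four contacts, P4 = 0.90, with a range of 0.80 to 0.95. The basis is protocol section 2.3.2: "nearly 90% of children receiving all four monthly SMC courses during the first and second years of the study". This is a proxy. It is receipt rather than attendance at the first contact of the month, it is a statement about the trial as a whole in years 1 and 2, and under section 7.5 a missed day can be made good: "Home visits are made to children who miss treatment on the designated day".
- Vaccination in the year, 0.90, independent of SMC attendance. The basis is Burkina Faso in 2019, also section 2.3.2: "90% received their second booster dose in June 2019".
- Equal and independent attendance at each contact, relaxed in step 4.

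Attendance per contact is p = P4^(1/4), and the probability of attending all five is p^5. The children whom the literal count admits and an all-five rule excludes are those who attend the first four and miss the fifth, a share of P4 − p^5.

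| P4 | p | p^5 | P4 − p^5 | × 0.90 vaccinated |
|---|---|---|---|---|
| 0.80 | 0.9457 | 0.7566 | 0.0434 | 0.0391 |
| 0.90 | 0.9740 | 0.8766 | 0.0234 | 0.0211 |
| 0.95 | 0.9873 | 0.9379 | 0.0121 | 0.0109 |

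**4. Clustered misses.** Some children probably miss repeatedly. A beta-binomial model with P4 held at 0.90 gives:

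| Intra-child correlation | All five | Extra admitted | × 0.90 vaccinated |
|---|---|---|---|
| 0.2 | 0.8846 | 0.0154 | 0.0139 |
| 0.5 | 0.8911 | 0.0089 | 0.0081 (from the unrounded extra) |

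So the central figure is 2.1 percentage points of the younger Burkina Faso children, falling to 1.4 or 0.8 points when misses cluster.

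**The case against.** The strongest reply is that the section already supplies the operative rule. It states in words that every SMC contact must be attended, protocol section 10.2 says the same of doses, and the authors plainly knew of the fifth course. The bracket then does harm only if someone codes it in preference to the words around it. This is a fair reading of intent, and I share it. It does not remove the contradiction, which should be settled before the analysis programmes are final.

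A second reply is that the consequence is negligible, and that mostly stands. A rough head count supports it. Protocol section 10.2 gives 3860 of 5920 children as ineligible in 2021, which leaves 2060, or 34.8%. Applied to the 2410 Burkina Faso children who consented to the extension, this gives 2060/5920 × 2410 ≈ 839 younger children. At 2.11 points that is about 18 children, or 6 per arm. Section 7.6.9 puts the ineligible share at about 60%, which would give 0.40 × 2410 = 964 and about 20 children. Both figures assume the same age split in each country and no further losses. The documents do not state the actual number of younger Burkina Faso children followed in 2021, so this indicates scale only.

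A third reply is that the size depends on how the bracket is coded. If any four of the five contacts sufficed, the extra share at P4 = 0.90 under independence would be 0.9936 − 0.8766 = 0.1170, or 0.105 after vaccination (0.1170 × 0.90). That is correct. It means the 2.1 points hold for the first-four reading only, and it shows that the text does not fix the derivation.

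Finally, the schematic entry has no bearing on the per-protocol rule. That also stands; it is listed only because it is wrong and easily corrected.

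**Conclusion.** The point holds, as a minor one. The SMC count in the SAP per-protocol rule is wrong for Burkina Faso in 2021 and conflicts with the wording around it. On the first-four reading, the literal count would enlarge the Year 5 per-protocol set by about 2.1 percentage points of the younger Burkina Faso children. The range is 1.1 to 3.9 points as attendance at the first four contacts runs from 95% down to 80%, and 1.4 or 0.8 points with clustered misses. These sizes rest on proxy attendance and vaccination rates; the inconsistency itself needs no assumption.

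The effect is confined to a secondary analysis, one year, one country and the younger children. The rule applies equally to all three groups, and I claim no bias in any hazard ratio.

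**What to change.** In the SAP section Per Protocol Analysis, replace the bracketed SMC count with: *all contacts scheduled for that country and year (5 in Burkina Faso in 2021, otherwise 4)*. Check the derivation program against this wording before the randomisation code is broken. In the protocol's Schematic of Study Design, correct the combined group's Burkina Faso entry for 2021 from five courses of SMC placebo to five courses of SMC.

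The cost is one phrase, one program check and one table entry. Data collection, the modified intention-to-treat analysis and power do not change. The only downside is a slightly smaller Year 5 per-protocol set in Burkina Faso than the literal first-four count would give, by the margin estimated above.

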There will be approximately 4,100 child-years of observation in the year following the third booster; 1367 child-years in each study group. Assuming the incidence of clinical episodes of malaria remains at about 200 episodes per 1,000 children per year during this period, the study will have 90% power, through a standard superiority comparison, to detect a 25.9% or greater relative difference (absolute difference: 52 cases per 1000 child-years) between the RTS,S/AS01E + SMC and the RTS,S/AS01E alone or SMC alone group. In the same period, the study will have 90% power, using a two sided 95% confidence interval, to exclude a 39.2% relative difference (absolute difference: 78 cases per 1000 child-years) in the incidence of clinical malaria between children in the RTS,S/AS01E alone or SMC alone group, using a non-inferiority design.

A similar analysis will be undertaken for the final year of the study following administration of a fourth booster dose of the RTS,S/AS01E or comparator vaccine but study power will be reduced because slightly more than half of the children enrolled (3860/5920) will not be eligible for SMC in 2021-22, and thus will not contribute further events nor person-time at risk to the study period.

Both intention-to-treat and per-protocol analyses will be undertaken. Children who received any dose of SMC or vaccine will be included in the intention to treat analysis. Children who received all scheduled doses of SMC, or who were treatment for a clinical episode of malaria at a time when SMC would have been given, or all scheduled doses of vaccine will be included in the per protocol analysis for each year of the study. Results obtained in Burkina Faso and Mali will be analysed separately. Additional sub-analyses will include analysis by age, gender, and bed net use during the transmission season, as determined by the history obtained at the cross-sectional surveys.

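### The SAP per-protocol rule drops for a whole year a child not seen at an SMC round because of malaria treatment, whereas protocol 10.2 keeps that child

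*Combined protocol and SAP*

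**What the plan says.** **SAP, Per Protocol Analysis.**
- The unit is the child-year: "The PP population will be defined separately for each year of the study".
- On the SMC side, per-protocol children are those who "were also seen at the first SMC/SMC placebo contact each month". The rule is restated for all three arms: "to be considered as per protocol, a child must have received all doses of vaccine AND attended all SMC contacts".
- The only malaria exception is for attenders: "Children who attended for SMC administration but who did not receive SMC because they had malaria and were referred for treatment will be included".
- Attendance rather than receipt is used because "the primary outcome of the trial (clinical malaria) can result in a specific SMC dose being missed permanently".
- Per protocol is a secondary analysis of the primary outcome. mITT is primary.

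**Protocol 10.2.** The yearly per-protocol set includes children who received every scheduled SMC dose, "or who were treatment for a clinical episode of malaria at a time when SMC would have been given". Nothing is said about attending the round.

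**Protocol 7.5.** "Home visits are made to children who miss treatment on the designated day", and SMC is given at home if the family agrees. The SAP does not say whether such a visit makes the child seen or attending.

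**The concern.** The two rules classify the same child differently. Uncomplicated cases are treated at health centres, some in Bougouni by community health workers, and severe cases in the district hospital (protocol 4.1). SMC is given at a central point in each community (protocol 7.5). A child can therefore be under malaria treatment in one place while a round takes place in another.

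Under the SAP that child fails the attendance condition. The whole year is lost, including the episode that caused the absence and any others. The SAP's own reason for preferring attendance to receipt, that malaria can cause a missed SMC dose, applies equally to the child whom malaria kept away. The exception covers only part of the problem it names, and the SAP does not explain why it is narrower than protocol 10.2.

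At stake is a per-protocol set selected partly on the outcome being analysed. Its incidence rates would be too low, and its hazard ratios could be disturbed if the selection differs between arms.

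**Working it through.** **1. The rules side by side**

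| Child with malaria when a round is due | Protocol 10.2 | SAP |
|---|---|---|
| Attended, referred, not dosed | In | In |
| Missed the day, seen at a home visit | In | Not stated |
| Not seen (e.g. inpatient) | In | Out for the year |

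The conflict is in the last row. The middle row is an ambiguity.

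**2. Size.** The plan gives no figure for this group, so what follows is an illustration.

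Inputs from the SAP (sample size section): SMC efficacy of 85% over four months, which hold 60% of annual cases without intervention. Taking unprotected annual incidence as 1, SMC alone has 0.60 × 0.15 + 0.40 = 0.49. That is 51% annual efficacy and reproduces the SAP's figure of at least 50%.

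Assumptions not in the documents:
- four rounds 30 days apart, so the seasonal hazard is h = 0.60/120 = 0.005 per day;
- a child treated in the five days before a round is absent with probability q = 0.10 to 0.50;
- the hazard before round 1 is g = 0.3 to 1.0 times the seasonal hazard, with no SMC protection from that year yet;
- RTS,S protection is constant over the year;
- SMC efficacy from day 22 of each interval is e = 0.50 to 0.85. The value 0.85 means no waning. The value 0.50 is the lowest compatible with a mean of 0.85, since days 1-21 would then need (0.85 × 30 - 0.50 × 9)/21 = 1.00.

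The share of an arm's episodes that fall in the days before a round is:
- RTS,S alone: f_R = h(5g + 15)
- SMC alone: f_S = h(5g + 15(1 - e))/0.49

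With Poisson episodes, dropping every child who has a round-missing episode multiplies per-protocol incidence by 1 - q·f. The RTS,S:SMC ratio is multiplied by (1 - q·f_R)/(1 - q·f_S).

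At q = 0.50:

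| g | e | f_R | f_S | Fall, RTS,S alone | Fall, SMC alone | Ratio multiplied by |
|---|---|---|---|---|---|---|
| 0.3 | 0.85 | 0.0825 | 0.0383 | 4.1% | 1.9% | 0.978 |
| 1.0 | 0.85 | 0.1000 | 0.0740 | 5.0% | 3.7% | 0.986 |
| 0.3 | 0.50 | 0.0825 | 0.0918 | 4.1% | 4.6% | 1.005 |
| 1.0 | 0.50 | 0.1000 | 0.1276 | 5.0% | 6.4% | 1.015 |

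At q = 0.10 the falls are 0.4-1.3% and the ratio factor is 0.996-1.003.

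A simulation with 3% background absence per round, a five-day window and the same range of q gives a fall of about 0.3-6% per arm and a ratio shift of about -3% to +1%. Adding between-child frailty (gamma, variance 1) at q = 0.50 and 305 episodes per 1000 child-years in both arms gives ratio factors of about 0.975 to 1.018. With e = 0.50 it removes 7.3-9.6% of episodes in SMC alone against 6.6-7.7% in RTS,S alone.

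**3. Does the protocol 10.2 rule create its own bias?** It keeps treated children who would have missed the round anyway. With background absence b = 0.03, window episodes are over-weighted by 1/(1 - b) - 1 = 0.031. The upward bias is 0.031 × f, which is 0.1% at f = 0.0383 and 0.4% at f = 0.1276. The simulation gives about +0.1 to +0.7%.

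**The case against.** **Direction.** A reader might infer that, because RTS,S alone probably has more malaria in the SMC months, more of its episodes are lost and the bias favours non-inferiority. The documents do not support this. What matters is the share of each arm's episodes in the days just before a round. Those are the days when SMC protection has had longest to wane. Before round 1, SMC-alone children have no SMC cover from that year, while RTS,S recipients were boosted in June. The table shows the sign reversing with the waning curve, which the documents do not give. This objection stands.

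**Home visits.** An outpatient case at home may be visited and so may count as seen. This stands as a limit on size. The clear remainder is inpatients and children not found.

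**Role of the analysis.** The SAP calls per protocol secondary and does not mention it in the non-inferiority rule. This stands. No decision in the plan is said to depend on it.

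**Not every treated case is the primary outcome.** The endpoint needs 5,000 parasites per µl or more, so some dropped children had malaria below it. This stands.

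**Protocol wording.** The sentence in 10.2 is garbled and does not expressly waive attendance, and protocol 10.1 leaves detail to the SAP. This stands only in part. As written, 10.2 admits these children without an attendance condition, and the SAP narrows that without giving a reason.

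**The remedy also conditions on malaria.** Keeping absentees who had malaria while dropping other absentees raises incidence. That is true, but by about 0.1-0.7%, against a fall of 0.3-6% under the SAP rule with the same assumptions.

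**Conclusion.** The point holds, as a limited one. The SAP and protocol 10.2 disagree about a child not seen at a round because of malaria treatment. The SAP version removes some child-years because of malaria, often the primary outcome. Per-protocol incidence is biased downwards in each arm by about 0.3-6%, if 10-50% of children treated shortly before a round are not seen, and by less if home visits count as contacts. The RTS,S:SMC ratio shifts by roughly -3% to +1%, which is small against the 20% margin and of unknown sign.

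The absence rate, the window and the waning curve are all assumptions, so the documents do not fix the size. Two further inferences should be avoided. The SAP does not drop every child with malaria at a round, because attenders who were referred stay in. The primary mITT analysis is not affected.

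**What to change.** Align the SAP exception with protocol 10.2: a child with documented malaria treatment, outpatient or inpatient, when an SMC round was due counts as compliant for that round whether or not the child attended. State how many days around a round count as due. State also whether a home visit for a missed round counts as a contact.

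Censoring follow-up at the missed round is not a better route, because a miss caused by malaria makes that censoring informative.

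The cost is two or three sentences in the SAP and a link between SMC contact records and treatment records that are already held electronically. No new data are needed, and the change can be made before the randomisation code is broken. The downside is the very small upward bias from keeping treated children who would have missed the round in any case.
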